6.5.1 Prohibited Concomitant Medications

Participants are prohibited from receiving the following therapies during screening and while on treatment during the study:

- Concurrent anticancer therapies such as chemotherapy, TKIs, radiotherapy (with the exception of palliative radiotherapy as specified in Section 6.5), antitumor interventions (surgical resection, surgical debulking of tumor, etc.), or cancer immunotherapy.
- Concurrent other investigational drugs.

For participants who, in the assessment by the investigator, require the use of any of the aforementioned treatments for clinical management, continuation of the study medication, and further participation in the study must be discussed and agreed upon with the Sponsor.

If participants receive additional anticancer therapies, this will be judged to represent evidence of disease progression, and study medication will be discontinued. These participants should complete all off-treatment assessments and continue to be followed for survival in the Survival Follow-up Period.

Further information on the prohibited concomitant therapies for lenvatinib is included in the prescribing information.

6.5.2 Rescue Medications and Supportive Care

Participants should receive appropriate supportive care measures as deemed necessary by the treating investigator.

6.6 Dose Modification

Lenvatinib dose reduction and interruption for participants who experience lenvatinib-related toxicity will be in accordance with the dose modifications described in [Table 3](#). AEs will be graded using CTCAE v5.0.

Asymptomatic laboratory abnormalities, including Grade ≥ 3 abnormalities (eg, elevations of amylase and lipase) that are not considered clinically relevant by the investigator should be managed per institutional guidelines; continuation of treatment should be discussed with the Sponsor.

Dose reductions will occur in succession based on the previous dose. Each reduction is a 20% reduction from the previous dose. Once the dose has been reduced, it cannot be increased at a later date, unless the dose has been mistakenly decreased; in this situation, Sponsor's approval is required to increase the dose. An interruption of lenvatinib >28 days will require consultation between the investigator and the Sponsor and written documentation of the collaborative decision on participant management.

Table 3 Criteria for Temporary Discontinuation of Study Drug, Dose Reduction, and Resumption of Treatment

Dose Modification Guidelines for Lenvatinib-Related Toxicity		
Treatment-Related Toxicity^{a,b}	Management	Dose Adjustment
Grade 1 or Tolerable Grade 2		
	Continue treatment	No change
Intolerable Grade 2^{c, d} or Grade 3^e		
First occurrence	Interrupt lenvatinib until resolved to Grade 0-1 or tolerable Grade 2	11.2 mg/m ² (or 20% reduction of the starting dose) orally QD (1-level reduction)
Second occurrence (same toxicity or new toxicity)	Interrupt lenvatinib until resolved to Grade 0-1 or tolerable Grade 2	9.0 mg/m ² (or 20% reduction of the previous dose) orally QD (1-level reduction)
Third occurrence (same toxicity or new toxicity)	Interrupt lenvatinib until resolved to Grade 0-1 or tolerable Grade 2	7.2 mg/m ² (or 20% reduction of the previous dose) orally QD (1-level reduction)
Fourth occurrence (same toxicity or new toxicity)	Interrupt lenvatinib	Discuss with Sponsor
Grade 4^f: Discontinue Study Treatment		
Abbreviations: BMI = body mass index; CTC = Common Toxicity Criteria; CTCAE = Common Terminology Criteria for Adverse Events; QD = once daily. Note: For grading, see CTCAE version 5.0. Collect all CTC grades of adverse events, decreasing and increasing grade.		
a An interruption of study treatment > 28 days will require Sponsor's approval before treatment can be resumed. b Initiate optimal medical management for nausea, vomiting, hypertension, hypothyroidism, and/or diarrhea prior to any study treatment interruption or dose reduction. c Applicable only to Grade 2 toxicities judged by the participant and/or physician to be intolerable. d Obese participants with weight loss do not need to return to the baseline weight or 10% of baseline weight (ie, Grade 1 weight loss). These participants will restart lenvatinib at a lower dose once their weight remains stable for at least 1 week and they reached the normal BMI (if the weight loss occurred, but it is still above normal BMI, they can restart lenvatinib at a lower dose once the weight has been stable for at least 1 week). Normal BMI should be used as the new baseline for further dose reductions. Refer to Appendix 13 for BMI-for-age percentiles. e For asymptomatic laboratory abnormalities, such as Grade ≥3 elevations of amylase and lipase that are not considered clinically relevant by the investigator, continuation of treatment should be discussed with the Sponsor. f Excluding laboratory abnormalities judged to be non-life-threatening, in which case manage as Grade 3.		

6.6.1 Blood Pressure

For children, BP varies by the sex and age of the child and it is closely related to height and weight. BP will be assessed in terms of percentile for sex, age, and height/length. Guidelines to sex, age, and height/length-specific percentiles of BP are provided in Appendix 11 and Appendix 12. BP that is consistently above the 95th percentile based on sex, age, and height/length (or BP $\geq 140/90$ mm Hg for participants 18 to 21 years old) requires further evaluation. A referral to a cardiologist is recommended for participants who develop hypertension during the study. Ideally, cardiovascular assessments and the management of hypertension should be supervised by a cardiologist. Exercise, excitement, coughing, crying, and struggling may raise the systolic pressure of children as much as 40 to 50 mm Hg greater than their usual level. Variability in BP in children of approximately the same age and body build should be expected, and serial measurements should always be obtained when evaluating a participant with hypertension. **BP values for the management of hypertension for participants 18 to 21 years old are included in parentheses in Section 6.6.2.**

6.6.2 Management of Hypertension

Hypertension is a recognized side-effect of treatment with drugs inhibiting VEGF signaling. Investigators should therefore ensure that participants enrolled to receive treatment with lenvatinib have BP <95th percentile (BP $\leq 150/90$ mm Hg) for sex, age, and height/length at the time of study entry and, if known to be hypertensive, have been on a stable dose of antihypertensive therapy for at least 1 week before Cycle 1 Day 1. Early detection and effective management of hypertension are important to minimize the need for lenvatinib dose interruptions and reductions.

Regular assessment of BP should be conducted as detailed in the SoA (Section 1.3). Hypertension will be graded using CTCAE v5.0, based on BP measurements only (and not on the number of antihypertensive medications).

If the participant's first BP measurement of the current assessment is elevated (systolic BP ≥ 95 th percentile [BP ≥ 140 mm Hg] or diastolic BP ≥ 95 th percentile [BP ≥ 90 mm Hg]), the BP measurement should be repeated approximately 5 minutes later. The mean value of 2 measurements approximately 5 minutes apart is defined as 1 BP assessment. If the BP assessment (ie, the mean of the 2 BP measurements obtained at approximately 5 minutes apart) is elevated (systolic BP ≥ 95 th percentile [BP ≥ 140 mm Hg] or diastolic BP ≥ 95 th percentile [BP ≥ 90 mm Hg]), a confirmatory assessment should be obtained at least 30 minutes later by performing 2 measurements (at approximately 5 minutes apart) to yield a mean value (Figure 2).

Antihypertensive agents should be started as soon as elevated BP (systolic BP ≥ 95 th percentile [BP ≥ 140 mm Hg] or diastolic BP ≥ 95 th percentile [BP ≥ 90 mm Hg]) is confirmed on 2 assessments obtained 30 minutes apart. The choice of antihypertensive treatment should be individualized to the participant's clinical circumstances and follow standard medical practice. For previously normotensive participants, monotherapy with one of the classes of antihypertensives should be started when systolic BP ≥ 95 th percentile (BP ≥ 140 mm Hg) or

diastolic BP \geq 95th percentile (BP \geq 90 mm Hg) is first observed on 2 assessments obtained 30 minutes apart. For those participants already on antihypertensive medication, treatment modification may be necessary if hypertension persists.

Lenvatinib should be withheld in any instances where a participant is at imminent risk to develop a hypertensive crisis or has significant risk factors for severe complications of uncontrolled hypertension (eg, BP \geq 99th percentile [BP \geq 160/100 mm Hg], significant risk factors for cardiac disease, intracerebral hemorrhage, or other significant comorbidities). Once the participant has been on the same antihypertensive medications for at least 48 hours and the BP is controlled, lenvatinib should be resumed as described below.

During the treatment period, participants with systolic BP \geq 99th percentile (BP \geq 160 mm Hg) or diastolic BP \geq 99th percentile (BP \geq 100 mm Hg) must have their BP monitored on Day 15 (or more frequently as clinically indicated) until systolic BP has been $<$ 95th percentile (\leq 150 mm Hg) and diastolic BP has been $<$ 95th percentile (\leq 95 mm Hg) for 2 consecutive treatment cycles. If a repeat event of systolic BP \geq 99th percentile (BP \geq 160 mm Hg) or diastolic BP \geq 99th percentile (BP \geq 100 mm Hg) occurs, the participant must resume the Day 15 evaluation until systolic BP has been $<$ 95th percentile (\leq 150 mm Hg) and diastolic BP has been $<$ 95th percentile (\leq 95 mm Hg) for 2 consecutive treatment cycles.

The following guidelines should be followed for the management of systolic BP \geq 99th percentile (BP \geq 160 mm Hg) or diastolic BP \geq 99th percentile (BP \geq 100 mm Hg) confirmed on repeat measurements after at least 30 minutes:

[figure not shown]
- Continue lenvatinib and institute antihypertensive therapy for participants not already receiving antihypertensive medication.
- For those participants already on antihypertensive medication, the dose of the current agent may be increased, if appropriate, or 1 or more agents of a different class of antihypertensive should be added.
- If systolic BP \geq 99th percentile (BP \geq 160 mm Hg) or diastolic BP \geq 99th percentile (BP \geq 100 mm Hg) persists despite maximal antihypertensive therapy, then lenvatinib administration should be interrupted and restarted at a lower dose QD (1 dose level reduction [20%] as specified in [Table 3](#)) only when systolic BP $<$ 95th percentile (BP \leq 150 mm Hg) and diastolic BP $<$ 95th percentile (BP \leq 95 mm Hg) and the participant has been on a stable dose of antihypertensive medication for at least 48 hours.
 - If systolic BP \geq 99th percentile (BP \geq 160 mm Hg) or diastolic BP \geq 99th percentile (BP \geq 100 mm Hg) recurs on the first dose reduction despite optimal management of hypertension with antihypertensive medications (either by dose increase or the addition of a different class of antihypertensive), then lenvatinib administration should be interrupted and restarted at an additional dose reduction only when systolic BP $<$ 95th percentile (BP \leq 150 mm Hg) and diastolic BP $<$ 95th percentile

- (BP \leq 95 mm Hg) and the participant has been on a stable dose of antihypertensive medication for at least 48 hours.
- If systolic BP \geq 99th percentile (BP \geq 160 mm Hg) or diastolic BP \geq 99th percentile (BP \geq 100 mm Hg) recurs on the second dose reduction despite optimal management of hypertension with antihypertensive medications (either by dose increase or the addition of a different class of antihypertensive), then lenvatinib administration should be interrupted and restarted at a third dose reduction only when systolic BP $<$ 95th percentile (BP \leq 150 mm Hg) and diastolic BP $<$ 95th percentile (BP \leq 95 mm Hg) and the participant has been on a stable dose of antihypertensive medication for at least 48 hours.
 - Additional dose reduction should be discussed with the Sponsor.

The following guidelines should be followed for the management of Grade 4 hypertension (life-threatening consequences):

- Institute appropriate medical management
- Discontinue lenvatinib

Figure 2 Procedures Associated with Management of Hypertension

Abbreviations: BP blood pressure; HTN hypertension; Tx treatment.

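### Section 6.6.2 gives opposite first instructions, withhold and continue, for a confirmed blood pressure at or above the 99th percentile in participants not already on antihypertensives

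*Combined protocol and SAP*

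**What the plan says.** Protocol Section 6.6.2 holds two rules that use the same blood pressure threshold.

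The withhold rule reads: "Lenvatinib should be withheld in any instances where a participant is at imminent risk to develop a hypertensive crisis". It adds a second trigger, joined by the word or: the participant "has significant risk factors for severe complications of uncontrolled hypertension". A parenthesis of examples follows. Its first item is blood pressure at or above the 99th percentile, and it runs on: "160/100 mm Hg], significant risk factors for cardiac disease, intracerebral hemorrhage, or other significant comorbidities". After at least 48 hours on the same antihypertensives, and once "the BP is controlled, lenvatinib should be resumed as described below".

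The guidelines further down cover systolic or diastolic pressure at or above the 99th percentile (160 or 100 mm Hg), "confirmed on repeat measurements after at least 30 minutes". They give three steps:

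- The untreated come first: "Continue lenvatinib and institute antihypertensive therapy for participants not already receiving antihypertensive medication".
- The already treated come next: "For those participants already on antihypertensive medication, the dose of the current agent may be increased, if appropriate". Adding agents of another class is the alternative.
- If pressure at that level "persists despite maximal antihypertensive therapy, then lenvatinib administration should be interrupted and restarted at a lower dose QD". Later bullets deal with recurrence after a first and a second reduction.

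Section 6.6.1 explains that the values in parentheses in Section 6.6.2 are for ages 18 to 21; younger participants are judged by percentile. Footnote b of Table 3 (Section 6.6) asks for optimal medical management of hypertension before any interruption or reduction.

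**The concern.** A toxicity rule should give one first action for one confirmed finding. Here the same threshold appears under both withhold and continue, with nothing to tell a site which governs. Two sites could each follow the text, one stopping lenvatinib at a first confirmed reading and the other carrying on while starting an antihypertensive.

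The first stake is safety in children and young adults on a drug for which the protocol itself calls hypertension a recognized side effect. The second is smaller: Section 9.12 summarizes exposure by number of cycles and by days on which medication is received, and days received would partly reflect how each site read the text.

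**Working it through.** No arithmetic decides this point. The check is to set the two rules side by side.

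1. **Threshold.** Both use the 99th percentile, with 160 and 100 mm Hg for ages 18 to 21.
2. **Confirmation.** The guidelines require it after at least 30 minutes; the withhold sentence states no such step. This does not separate the rules, because a confirmed reading meets both.
3. **First action.** One rule withholds. The other continues lenvatinib and starts antihypertensive therapy.
4. **Who is covered.** The withhold sentence applies to any participant. The continue bullet applies only to those not already on antihypertensives. For those already treated, the bullet adjusts their antihypertensives and mentions neither continuing nor withholding. Interruption appears only in the next step, after maximal therapy has failed, so continuing is implied but not stated.
5. **Resumption.** The withhold rule sends the reader to the text below. That text gives a restart dose only after persistence or recurrence, and in each case it is a reduced dose. The dose after a first hold that meets neither condition is not given. This matters because Section 6.6 does not allow a reduced dose to be raised again, unless the reduction was a mistake and the Sponsor approves.
6. **Table 3.** Footnote b puts medical management ahead of any interruption, which differs from withholding outright. The table otherwise works by CTCAE grade, and the documents do not map the 99th percentile to a grade, so it does not settle the matter.
7. **Priority.** No sentence ranks the rules or divides the readings between them.

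Worked case: a 19-year-old not on antihypertensives has a confirmed 165/105 mm Hg. Since 165 ≥ 160 and 105 ≥ 100, the reading matches the withhold example and falls within the continue bullet.

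Frequency: the documents bound this only indirectly.

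- Section 4.3 reports three dose-limiting toxicities at 14 mg/m² in Study 207. One was Grade 3 hypertension and one was Grade 4. Grade 4 has its own rule in Section 6.6.2 (discontinue) and lies outside the conflict, leaving 2 − 1 = 1 relevant event.
- Section 2.2.1.2 says that the only Grade 3 or higher events seen in more than 2 of the 31 expansion-cohort participants were back pain and tumor pain. Grade 3 or higher hypertension therefore occurred in at most 2: 2/31 = 6.5%.
- The same section puts treatment-related hypertension at 30% or more, without restriction by grade. It does not measure pressure at or above the 99th percentile.

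**The case against.** The best defense is that the two rules were meant for different situations. The operative test for withholding is imminent crisis or significant risk of severe complications, and the pressure value only illustrates that test. A first confirmed reading in an untreated participant is arguably not yet uncontrolled hypertension. The guidelines are the more specific text, the withhold sentence defers to them for resumption, and Section 6.6.2 says it wants to keep interruptions to a minimum. On that view the pressure value counts only together with further risk.

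This reading is plausible, but it is not written. The examples are separated by commas and the word or, and the pressure value is not made conditional on the others. A site that withholds at that value is following the sentence as it stands.

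Figure 2 might separate the cases. It is not shown here and cannot be checked, but even a clear figure would leave the conflicting text in place.

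Three stronger inferences should be resisted:

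- **That the explicit clash covers everyone.** The continue wording is limited to participants not already on antihypertensives.
- **That the conflicting branch will be reached often.** A reader might infer this from two hypertension events among three dose-limiting toxicities, or from the 30% figure. One of those events was Grade 4 and has its own rule, and the 30% figure covers all grades.
- **That dose-intensity results or the primary analysis are compromised.** Section 9.12 plans cycles and days of exposure, with no dose-intensity summary. The primary analysis estimates Week 16 response within each tumor type in a single-arm study, and the documents show no effect of this wording on it.

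**Conclusion.** The point holds. As worded, Section 6.6.2 gives opposite first actions for one confirmed blood pressure in participants not already on antihypertensives. It implies the same conflict for those already treated, and it leaves resumption after a first hold incomplete.

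The overlap rests on the text alone. Taking the pressure value as enough to withhold assumes that the examples are read as listed; the narrower reading is possible but unstated, and the existence of both readings is itself the problem. The size is uncertain: the frequency of pressure at or above the 99th percentile is not given, and the nearest figures are one Grade 3 dose-limiting event at 14 mg/m² and at most 2 of 31 with Grade 3 or higher hypertension in the expansion cohort. The consequence is inconsistent management of a known toxicity and some site dependence in days of exposure. It should be corrected for safety even if the branch is seldom reached.

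**What to change.** Reconcile the two passages in Section 6.6.2 so that one confirmed blood pressure leads to one instruction, both for participants not on antihypertensives and for those already taking them. If the withhold sentence is meant only for that pressure together with further risk, say so. State how lenvatinib is resumed after a first hold. Check that Table 3 footnote b and Figure 2 agree with the result. Which instruction applies is for the sponsor's clinical team to decide; this review takes no position on it.

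The cost is a wording clarification in the protocol and a letter to sites. No change to the sample size, endpoints or analyses is needed.

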6.6.3 Management of Proteinuria

Regular assessment for proteinuria should be conducted as detailed in the SoA (Table 1). Guidelines for assessment and management of proteinuria are summarized as follows:

Grading of Proteinuria

- Grading according to CTCAE v5.0 will be based on the protein-creatinine ratio or 24-hour urinary protein result if available. For participants ≥18 years of age, if the participant has 4+ proteinuria by dipstick (≥1000 mg/dL by urinalysis), a 24-hour urinary protein result is required to confirm Grade 3 proteinuria.

Management of Proteinuria

- Management of lenvatinib administration will be based on the grade of proteinuria according to Table 3.

- In the event of nephrotic syndrome, lenvatinib must be discontinued.

Detection and Confirmation

- Perform urine dipstick testing per the SoA (Table 1). Urine dipstick testing is the preferred method for testing for urinary protein, however, urinalysis may be used if the use of urine dipsticks is not feasible.
- For participants ≥ 18 years of age, a 24-hour urine collection (initiated as soon as possible and at least within 72 hours) or an immediate spot P/C test AND for participants < 18 years of age, an immediate spot P/C test, and if possible, a 24-hour urine collection (initiated as soon as possible and at least within 72 hours) is required in the following situations:
 - The first (initial) occurrence of $\geq 2+$ (≥ 100 mg/dL) proteinuria on urine dipstick (or urinalysis) while on lenvatinib.
 - A subsequent increase in severity of urine dipstick or urinalysis proteinuria occurring on the same lenvatinib dose level.
 - When there has been a lenvatinib dose reduction and at the new dose level the urine protein dipstick result is $\geq 2+$ (≥ 100 mg/dL).

Note: For participants ≥ 18 years of age, a 24-hour urine collection (initiated as soon as possible and at least within 72 hours) to verify the grade of proteinuria is required when P/C test is ≥ 2.4 .

Monitoring

- Urine dipstick or urinalysis testing for participants with proteinuria $\geq 2+$ (≥ 100 mg/dL) should be performed on Day 15 (or more frequently as clinically indicated) until the results have been 1+(10 mg/dL) or negative for 2 consecutive 28-day treatment cycles.
- Proteinuria monitoring can be performed at the local laboratory or investigator site but must be managed by the site physician.

6.6.4 Management of Gastrointestinal Symptoms and Acute Abdominal Pain

Initial management of acute abdominal pain in these study participants should be focused on treating the underlying cause where possible, ensuring appropriate hydration/rehydration, and symptomatic pain improvement consistent with participant's age and in accordance with local and institutional standards of care. Appropriate supportive care should be provided together with close monitoring.

For AEs of abdominal pain believed related to lenvatinib or more specific AEs believed related to lenvatinib that result in the symptom of abdominal pain, follow instructions

contained in [Table 3](#) regarding lenvatinib dose reduction and interruption. For Grade 4 AEs that result in abdominal pain, lenvatinib must be discontinued.

GI symptoms including diarrhea should be managed by providing symptomatic treatment. If the symptoms persist (eg, diarrhea for more than 10 days), guidelines in [Table 3](#) should be followed. GI symptoms should be monitored closely and evaluated using CT, contrast-enhanced MRI, ultrasound, or other diagnostic imaging if clinically indicated, at the investigator's discretion.

